5.4.4 Management of rash

A proactive and early approach to management of rash is crucial. Rash can be managed by a variety of treatment options to relieve symptoms and reduce the rash. The recommendations for management are as follows:

Table 4 : Management of rash

CTCAE v4.0 Grade	Recommended management	Dose adjustment
No event	General/Prevention: strict sun protection; use of a sunscreen of Sun Protection Factor 15 (SPF 15) or higher, preferably containing zinc oxide; use of a thick, alcohol-free emollient cream; avoid harsh detergents, avoid using a solarium.	Trial treatment to be continued without dose delay/reduction.
Rash Grade 1	Mild rash may not need treatment. However, if treatment is considered necessary, topical hydrocortisone (1% or 2.5%) cream and/or clindamycin 1% gel can be used.	Trial treatment to be continued without dose delay/reduction.
Rash Grade 2	Relief from major symptoms caused by grade 2 skin related adverse events should be achieved by a combination of local and systemic therapies including: 1) Systemic antibiotics (e.g. doxycycline or minocycline) 2) Topical treatment (hydrocortisone 2.5% cream, clindamycin 1% gel, pimecrolimus 1% cream) And / or 1) Antihistamines (e.g. diphenhydramine) 2) Oral prednisone (short term i.e., <14 days treatment) may be added at investigator's discretion Systemic and topical treatment should be initiated at the start of grade2 and continue until resolution or improvement to grade ≤1.	If grade 2 rash persists for 7 days or more despite treatment and is poorly tolerated by the patient, the investigator may choose to hold afatinib up to 14 days until patient has recovered to grade ≤ 1 and resume at 20 mg.
Rash Grade 3	May be treated in a manner similar to grade 2 rash.	Hold afatinib up to 14 days until patient has recovered to grade ≤ 1 and resume at 20 mg.

Rash Grade 4	Same treatment as grade 2-3 is recommended. Additionally, use of IV antibiotics and/or steroids is recommended if clinically indicated. Consultation with dermatologist.	Discontinue afatinib. Do not re-challenge with afatinib
---------------------	---	--

5.4.5 Management of Interstitial Lung Disease (ILD)

Careful assessment of all patients with an acute onset and/or unexplained worsening of pulmonary symptoms (dyspnea, cough, fever) should be performed to exclude ILD.

Table 5 : Interstitial Lung Disease

CTCAE v4.0 Grade	Recommended management	Dose adjustment
Acute onset and/or unexplained worsening of pulmonary symptoms (dyspnea, cough, fever), any grade	Appropriate treatment instituted as necessary.	Afatinib should be held pending investigation of these symptoms.
Interstitial Lung Disease diagnosis (any grade)	Appropriate treatment instituted as necessary.	Discontinue afatinib. Do not re-challenge with afatinib.

5.4.6 Management of Protocol specified significant event: hepatic injury

The following event is defined as Protocol-specified significant event: **Hepatic injury** defined by the following alterations of liver parameters:

for patients with normal AST / ALT and bilirubin at baseline: an elevation of AST and/or ALT above >3 fold ULN combined with an elevation of bilirubin above >2 fold ULN measured in the same blood draw sample.

for patients with abnormal AST / ALT and bilirubin at baseline : an elevation of AST and/or ALT >5 fold ULN combined with an elevation of bilirubin >2 fold ULN measured in the same blood draw sample.

Table 6 : Management of hepatic injury

Event	Recommended management	Dose adjustment
AST and/or ALT above > 3 fold ULN combined with an elevation of bilirubin above > 2 fold ULN (patient with normal LFT at baseline) or AST and/or ALT above > 5 fold ULN combined with an elevation of bilirubin above >2 fold ULN (patient with abnormal LFT at baseline)	Promptly report the event to TRIO within 24 hours of learning its occurrence (see section 7.3). Monitor every week until liver chemistries resolve or return to within baseline values. A specialist or hepatology consultation is recommended.	Discontinue afatinib. Do not re-challenge with afatinib.

5.4.7 Other Adverse events

Table 7: Treatment schedule adjustments

Type and CTCAE v4.0 Grade of event	Dose adjustment
Any drug related AE grade ≥ 3 (except Left Ventricular Systolic Dysfunction which requires special instruction below)	Hold afatinib up to 14 days until patient has recovered to grade ≤ 1 and resume at 20 mg.
Acute kidney injury (renal dysfunction) grade ≥ 2 (Worsening of renal function grade ≥ 2 as measured by serum creatinine)	
Keratitis symptoms (such as acute or worsening eye inflammation, lacrimation, light sensitivity, blurred vision, eye pain and/or red eye), any grade	
Refer promptly to an ophthalmology specialist.
 
Hold afatinib during evaluation of suspected keratitis, up to 14 days until patient has recovered completely and resume at 20 mg.
 
If keratitis is diagnosed, benefits and risks of continuing treatment should be carefully considered. Medical Monitor/TRIO Medical Lead/Trial Chair should be contacted.
 
If diagnosis of ulcerative keratitis is confirmed, discontinue afatinib. Do not re-challenge with afatinib.

Any other drug related AE prolonged (≥ 7 consecutive days) grade 2 poorly tolerated by the patient.	Investigator may choose to hold afatinib up to 14 days until patient has recovered to grade ≤ 1 and resume at 20 mg.
Any unrelated (serious or not serious) adverse event	
Investigator may choose to hold afatinib up to 7 days until patient has recovered to grade ≤ 1 and resume at the same dose.
 
If the investigator chooses to pause the medication for more than 7 days and believes that the patient would derive clinical benefit from continuing medication, the decision to continue medication will be made by the trial medical monitor in agreement with the investigator.

Left Ventricular Systolic Dysfunction grade ≥ 3	Discontinue afatinib. Do not re-challenge with afatinib.

5.5 Concomitant Medications and Procedures

5.5.1 Supportive care

Medication intended solely for supportive care (analgesics, antidiarrheals, antibiotics, antidepressants, etc.) may be used at the investigator's discretion. Erythropoietin and/or blood products may be used at the investigator's discretion for the supportive treatment of anemia.

5.5.2 Precautions – Treatment interaction with P-gp

There is no treatment interaction with letrozole.

Afatinib is a substrate of P-gp and its plasma concentrations can be affected by the use of P-gp inhibitors and it is also likely that P-gp inducers could also influence afatinib plasma concentrations. The use of potent P-gp inhibitors and potent P-gp inducers has to be avoided during treatment with afatinib.

For patients who require therapy with a P-gp inhibitor and who are receiving afatinib at a daily dose of 30 mg, afatinib dose may be reduced to 20 mg if not tolerated. If a P-gp inhibitor or inducer is planned to be administered to the patient, Medical Monitor/TRIO Medical Lead/Trial Chair should be contacted by the site prior to initiating therapy.

Table 8 below provides a non-exhaustive list of P-gp inhibitors or inducers to be avoided during trial treatment.

Table 8: Treatment interacting with P-gp

Strong P-gp inhibitors	P-gp inducers
Amiodarone	Carbamazepine
Clarithromycin	Phenobarbital
Cyclosporin	Phenytoin
Erythromycin	St John's wort
Ketoconazole	Rifampicin
Itraconazole	
Nelfinavir	
Quinidine	
Phenobarbital salt with Quinidine	
Ritonavir	
Tacrolimus	
Saquinavir	
Valspodar	
Verapamil	

This list is not meant to be considered all inclusive. See website for an available current list : <http://www.fda.gov/drugs/developmentapprovalprocess/developmentresources/druginteractionslabeling/ucm093664.htm>.

It is the investigator's responsibility to assess for potential drug interactions with afatinib and any P-gp inhibitor/inducer not listed above.

5.5.3 Surgery while on trial treatment

Based on the EGFR blocking mode of action, the risk that afatinib may interfere with skin wound healing process cannot be excluded. Therefore, interruption of afatinib should be considered before and after surgery to allow for adequate post-operative wound healing based on individual benefit/risk assessment. The maximum period of interruption for afatinib is 14 days. If interruption of greater than 14 days is required, treatment with afatinib should be discontinued.

5.5.4 Prohibited Treatments and/or Procedures

5.5.4.1 Local and/or systemic anticancer therapy

No additional local and/or systemic anticancer therapy will be permitted while patients are receiving trial therapy with the only exception of palliative radiotherapy (see section 5.5.3.3).

5.5.4.2 Bone-modifying agents

Bone-modifying agents (i.e. bisphosphonates, denosumab) may be continued for patients who are already receiving them at the time of randomization. However, the need to commence bone-modifying agents after randomization will be considered indicative of disease progression unless disease progression can be completely ruled out and bone-modifying agents treatment initiation is expressly agreed by the investigator in consultation with Medical Monitor/TRIO Medical Lead/Trial Chair.

Medical Monitor/TRIO Medical Lead/Trial Chair should be contacted by the site prior to initiating bone-modifying agents in this case.

5.5.4.3 Palliative radiotherapy

Palliative radiotherapy is permitted for the treatment of painful bony lesions providing the lesions were known to be present at the time of randomization and the investigator clearly indicates that the need for palliative radiotherapy is not indicative of disease progression. In view of the current lack of data about the interaction of afatinib with radiotherapy, afatinib treatment should be interrupted during palliative radiotherapy, stopping 1 day before and resuming treatment 1 week after. In case of afatinib discontinuation for more than 14 days then trial treatment should be discontinued.

6. SCHEDULE OF VISITS AND PROCEDURES

6.1 Patient Inclusion

6.1.1 Informed Consent

Prior to the screening evaluation, the patient or legally acceptable representative was informed of the nature of the trial treatments and was given pertinent information as to the intended purpose, possible benefits, and possible adverse experiences. The procedures and possible hazards to which the patient would be exposed were explained. A legally acceptable representative is an individual or other body authorized under applicable law to consent, on behalf of a prospective patient, to the patient's participation in the trial.

An approved patient informed consent form (PICF) was then read and signed by the patient, and, when required, a witness, and the investigator or a person designated by the investigator, as per local regulations. The patient was provided with a copy of the signed PICF.

Further to this protocol amendment, the patient or legally acceptable representative will receive an approved addendum to the patient informed consent form that should be read and signed. Indeed, this PICF addendum will inform the patient or legally acceptable representative that all patients will be discontinued from the trial by 30 November 2018 at the latest.. The patient will be provided with a copy of the signed PICF addendum.

The patient can withdraw from the trial at anytime without prejudicing future medical treatment. In any case, the withdrawal should be documented on the initial informed consent form, and must be dated and signed by patient and by the investigator.

If a potential patient or legally acceptable representative is illiterate or visually impaired, the investigator must provide an impartial witness to read the PICF to the patient and must allow for questions. Thereafter, both the patient or legally acceptable representative and the witness must sign the PICF to attest that informed consent was freely given and understood. The PICF will include a statement by which the patient allows the Sponsor's duly authorized personnel, the Ethics Committee (IRB/IEC), and the regulatory authorities to have direct access to their data, which will be processed according to the confidentiality regulations. In case important new information becomes available that may be relevant to the patient's consent and willingness to continue participation in the trial, the PICF will be revised and submitted to IRB/IEC for approval/favorable opinion. The new information will be discussed with the patient and if she agrees to continue participation in the trial, the revised PICF will be signed and dated and the patient will receive a copy.

This trial has an optional component described in the PICF, with a consent section dedicated to this optional trial. If a patient opted not to participate in the optional portion, this in no way affects the patient's ability to participate in the main research trial.

6.1.2 Registration/ Randomization

The treatment assigned was based on a dynamic minimization procedure using metastatic involvement (bone only YES or NO) and prior exposure to aromatase inhibitor (prior hormonal therapy YES or NO) as factors in the minimization algorithm. The ratio used was 1:1 and the randomization technique was using a stochastic treatment allocation algorithm based on the variance method.

The following steps for registering and randomizing a patient were chronologically performed:

The patient had to provide written informed consent prior to performing any trial specific procedure not considered standard practice by the institution.

The site registered the patient in the IWRS system (Date of ICF signed and patient year of birth needed). The system uniquely attributed a registration number to each patient in the trial. Each center was uniquely identified by a number assigned by TRIO to the investigative site. The site received a registration confirmation, containing patient registration number as well as HER2/Hormonal receptors screening form specific for the patient.

The site prepared a tumor sample fixated in formalin and embedded in paraffin (or 15 to 20 unstained slides) and shipped this sample along with the duly completed HER2/Hormonal receptors screening form to [name] laboratory (see contact details on Information Resources page - Central laboratory's address and contact details are pre-printed on the form). The tumor material can be returned to the site after testing upon site's request.

[name] laboratory entered in the IWRS system the HER2/Hormonal receptors results in a timely manner after receipt of the tumor material (usual turn-around-time was within 5 working days after receipt of the tumor material).

If (HER2-positive and/or H score not [1-159]) => The patient were moved to the Screen failure category.

If (HER2-negative and H-score [1-159]) => Screening of the patient continued at the site.

Upon completion of screening procedures and entry of screening data in TRIO eDC system, the investigator or his/her delegate checked if the patient met all eligibility criteria:

Patients who did not meet the eligibility criteria were moved to a screen failure category in the IWRS.

Patients who met all eligibility criteria were randomized in the IWRS using the following stratification factors:

Bone only disease : Yes versus No

Prior neo/adjuvant hormonal therapy : Yes versus No

Details regarding the Registration and Randomization processes were provided in the IWRS user manual and in the trial specific working instruction for Registration/Randomization.

Patients randomized in the trial had to start trial treatment within 7 days of randomization.

6.1.3 Blinding/Unblinding

The trial is open-label. There is no blinding of the treatment.

6.2 Trial Participation and Discontinuation

Once trial treatment is discontinued (both letrozole and afatinib) regardless of the reason, patients will be discontinued from the trial and will be followed and treated as per local clinical practice. If the patient withdraws from trial participation (consent withdrawn from trial, lost to follow-up, investigator's decision), no further trial procedures are performed, and no additional data will be collected. Medical care of the patient is not affected if the patient chooses to leave the trial at anytime.

Please refer to section 3-Trial Design (IN ADDITION) regarding the decision to discontinue the patients from the trial at the latest on 30 November 2018 and the conditions of this discontinuation.

6.3 Schedule of Procedures

All screening and baseline evaluations had to be completed prior to initiating trial treatments. Adherence to the schedule of assessments is required and visits should be planned accordingly. In the event a visit is missed because of an unforeseeable event, then the missed visit should be scheduled for the next day.

Prior to undergoing any trial specific procedures not considered standard practice by the institution, patients had to read and sign the consent form. All trial procedures are detailed in the Schedule of Activities table presented below.

According to the information reported in section 3-Trial Design (IN ADDITION) regarding the decision to discontinue the patients from the trial at the latest on 30 November 2018, the information reported in this section is applicable until 30 November 2018. After that date, the patients will be followed by their physician as per standard of care and the assessments will be performed as per local practice.

Table 9 : Schedule of activities

Protocol Activities	Pre-screening	Screening ¹ 28 days prior randomization	Treatment Period ²	End of treatment ³
Signed ICF ⁴	X			
Local determination of ER/HER2	X			
Tumor sample to central lab.	X			
Medical, surgical, disease history		X		
Signs and symptoms		X		
SAFETY			q4w	
Physical exam / Vital signs / PS		X	X	X
Review of adverse events		X	X	X
Hematology / Blood chemistry		X ^{5, 6}	X ⁶	X ⁶
LVEF		X within 42 days	X ⁷ q12w	X
TREATMENT			q4w	
Letrozole / Afatinib : Dispensation / Accountability			X	
EFFICACY			q12w	
Disease assessment		X	X	
Survival / Anticancer therapy				

¹¹ Pre-screening / Screening starts once the subject has signed the PICF.

² Visits are scheduled every 4 weeks +/- 3 days during treatment phase.

³ End of Treatment visit must be scheduled as close as possible to 30 days post last intake of any study drug or on 30 November 2018 whichever occurs first.

⁴ There is no window for obtaining the signed ICF. Study specific screening assessments not considered standard practice by the institution may start once the PICF has been obtained.

⁵ At screening only, Creatinine clearance will be assessed to check eligibility if serum creatinine $\geq 1.5 \times$ ULN.

⁶ During treatment phase, blood tests must be obtained up to 5 days prior to the visit and will assess the following parameters :

Hematology: Hemoglobin, Absolute Neutrophils Count (ANC), Platelets.

Blood chemistry: AST, ALT, Alkaline Phosphatase, Total Bilirubin and Creatinine.

⁷ LVEF will be assessed every 12 weeks during treatment phase and when clinically indicated.

6.3.1 Safety assessments

The following safety assessments were performed within 28 days of randomization of the patient and subsequently at each visit during treatment phase and at End of trial treatment visit. There was no need to repeat these safety assessments at Visit 1 since screening assessments were available, unless deemed clinically required by the investigator.

Physical exam: **included an examination of major body systems and weight.**

Vital signs: **blood pressure.**

Performance status (PS) **was assessed according to ECOG scale (APPENDIX 1).**

Blood tests:

Hematology: **Hemoglobin, Absolute Neutrophils Count (ANC) and Platelets.**

Blood chemistry: **AST, ALT, Alkaline Phosphatase, Total Bilirubin and Creatinine and Creatinine clearance (at baseline only).**

During treatment phase, blood tests may be obtained up to 5 days prior to the visit.

LVEF: will be obtained during screening and every 12 weeks during treatment phase, and as required when clinically indicated. LVEF will be performed by MUGA scan or echocardiogram, using the same method at each assessment.

6.3.2 Efficacy assessments

6.3.2.1 Schedule/details of tumor assessments

Screening/Baseline:

Baseline Disease assessment were performed during screening, within 28 days of randomization of the patient.

Disease assessment at screening was used to determine the nature of lesions (measurable versus non-measurable). Lesions must be clearly identified and documented as Target or Non-Target lesions as per RECIST 1.1.

Baseline assessment included at least:

- Baseline bone scan
- Other bone imaging had to be performed on bone lesions if the investigator intended to follow bone lesions with correlative imaging (e.g. CT with bone window, MRI or plain X-rays).
- CT or MRI scan of the chest, abdomen, and pelvis (CAP)
- Clinical assessment of superficial lesions (including measurement with calliper)
- Any additional imaging as deemed appropriate

Subsequent Disease assessments:

- Every 12 weeks (+/- 1 week) starting from date of randomization
- Whenever disease progression is suspected,
- To confirm a partial or complete response (at least 4 weeks after initial documentation of response). For patients with bone metastases identified at baseline bone scan is required at the time of confirmation of complete response.

Disease assessments will be performed until the end of treatment. The schedule of assessments should be fixed according to the calendar, regardless of treatment interruptions.

Disease assessments will comprise evaluation of all lesions identified at baseline, with the exception of bone lesions in some circumstances (see 6.3.2.2).

The same method of assessment and the same technique should be used to characterize each identified and reported lesion at baseline and during follow-up imaging.

Unless clinically required, it is not mandated to repeat imaging of an area where no lesion was documented at baseline.

Table 10 : Efficacy assessments

Baseline Within 28 days of randomization	Treatment phase until the End of Treatment
Bone scan CT or MRI of chest, abdomen and pelvis (CAP) Clinical assessment of superficial lesions Any additional imaging as deemed appropriate	Every 12 weeks +/- 1 week : repeat the CT/MRI and/or clinical assessment and/or any appropriate imaging used to document baseline lesions Confirmation of PR and CR: not less than 4 weeks after first documentation of response. Bone scan/bone imaging : 
 • when progression is suspected in bone • Bone scan for confirmation of CR (if bone metastases were identified at baseline).

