
Efficacy Assessments
	
Disease assessments every 12 weeks until documentation of progressive disease.
 
This is applicable until 30 November 2018. After that date, the patients will be followed by their physician as per standard of care and the efficacy assessments will be performed as per local practice.

Safety Assessments
	
Physical examination, blood tests (hematology and blood chemistry) before each visit (every month) during the treatment period.
 
LVEF every 12 weeks during the treatment period.
 
This is applicable until 30 November 2018. After that date, the patients will be

	followed by their physician as per standard of care and the safety assessments will be performed as per local practice.
Additional Assessments	None
Statistical Methods and Sample Size	N/A Due to the small number of patients enrolled in the trial, only a descriptive analysis will be conducted.

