In trial 1200.5 Afatinib PK parameters were within the ranges observed in afatinib monotherapy studies (PK meta-analysis [U10-1153]), suggesting that continuous dosing in combination with 2.5 mg letrozole had no major influence on afatinib PK. Mean PK parameters for letrozole showed no trend to higher or lower values in conjunction with afatinib dosing. The observed letrozole PK parameters were in the ranges reported in the literature ([R10-4018] and [R10-4019]), suggesting that afatinib did not have a relevant effect on letrozole PK. Therefore, there was no indication of a DDI between letrozole and afatinib and vice versa (when compared with literature or historical data). Based on this data it is not planned to further evaluate PK interactions in this combination.

A detailed section on the management of adverse events, among which diarrhea and rash, has been incorporated in the protocol with some proactive precautions to avoid occurrence or aggravation of these specific adverse events at a very early point.

Protocol amendment 4.0 was released on 09 May 2016 and its main change was the enrollment closure due to insufficient efficacy data to pursue development of afatinib in breast cancer and low recruitment in the trial. As of the date of release of this new protocol amendment, there are 6 patients still on treatment in the trial and among those, only 2 patients are treated with the combination of letrozole and afatinib (Arm B). Due to the limited number of patients still on treatment, and especially in Arm B, TRIO and BI agreed to release this amendment to discontinue the trial, allowing patients receiving afatinib to continue with this treatment outside of the TRIO-020 trial.

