- If the patients treated with the combination of afatinib and letrozole (arm B) discontinue the trial treatment (whatever the reason) before 30 November 2018, the patients from the other arm (arm A, letrozole alone) still on treatment will also be discontinued from the trial at the same time. They may continue receiving letrozole using commercial drug as standard of care according to their treating physician discretion.

[figure not shown]
- If the patients treated with afatinib and letrozole (arm B) have not discontinued the trial treatment by 30 November 2018, all patients currently on treatment in the trial (including the ones only treated by letrozole alone (arm A)) will be discontinued from the trial at that time. They may continue receiving their treatment if in alignment with their treating physician judgment as follows:
 - Patients in arm A: may continue receiving letrozole using commercial drug as standard of care according to their treating physician discretion.
 - Patients in arm B: may continue receiving afatinib in the context of an alternative drug supply outside the clinical trial as appropriate according to local legislation. Additionally, they may continue receiving letrozole using commercial drug as standard of care according to their treating physician discretion.
- Note; In case no alternative drug supply outside the clinical trial as appropriate according to local legislation can be put in place and the 2 patients in Arm B are still on treatment on 30 November 2018, the protocol and PICF will need to be revised again.

Once the patient is discontinued from trial treatment and has undergone the End of Treatment visit (see section 6.3), the patient will be permanently discontinued from the trial.

This trial also included an optional exploratory research component. This optional portion of the trial is a molecular profiling assay aimed to assess the relationship of antitumor activity with the expression of a few cell cycle-related proteins and other markers that may be identified in the future. (See section 2.3)

Patients participated in this trial even if they had chosen not to participate in the sample banking component.

Figure 1 : Trial Scheme - Patient Selection and Treatment

* As described in section 3-Trial Design (IN ADDITION)

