5. TREATMENT

5.1 Protocol Treatment

Eligible patients receive either oral letrozole 2.5 mg plus oral afatinib 30 mg daily or oral letrozole 2.5 mg daily until progression of disease or any other trial treatment discontinuation criteria as per section 5.3.3.

Treatment allocation was operated centrally after patients had given their written informed consent and had completed the necessary baseline assessments.

Refer to section 6.1.2 for registration and randomization process.

If a patient was randomized but did not receive any treatment, the reason was documented in the case report form (CRF). Patients remained on trial, baseline data was collected and follow-up continued. These patients will now be discontinued from the trial once their trial treatment is discontinued and they will be followed and treated as per local clinical practice.

Investigational Medicinal Product” (IMP), Non Investigational Medicinal Product” (NIMP):

According to the ICH Good Clinical Practice and EU Directive 2001/20/EC Article 2 (d), afatinib falls under the definition of Investigational Medicinal Product (IMP) while letrozole which is considered as Standard of Care (SoC) in this treatment population falls outside of this definition and is then to be considered as a “Non Investigational Medicinal Product” (NIMP).

Definition and management of IMP and NIMP are further described in a separate Trial Specific Guideline.

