6.3.2.2 Special note for baseline determination of Bone lesions and follow-up assessments

In presence of other measurable lesions, the bone lesions are not mandatory to follow. Nevertheless, if followed by imaging, the technique was selected by the site at baseline and will be repeated until documentation of disease progression.

In absence of any other measurable lesions, the bone lesions will be followed every 12 weeks with the most appropriate imaging technique selected by the site at baseline (CT with bone window or MRI or plain X-ray or bone scan) and repeated until documentation of disease progression.

Bone scan/bone imaging is required when progression is suspected in bone.

Bone scan is required at the time of confirmation of CR (if bone metastases were identified at baseline).

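### Do two different stated ends of tumour assessment leave PFS and TTP censoring undefined, or different by arm?

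*Protocol*

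**What the plan says.** **End of imaging.** Section 6.3.2.1 states "Disease assessments will be performed until the end of treatment", and the heading of Table 10 agrees. The synopsis (Efficacy Assessments) states "Disease assessments every 12 weeks until documentation of progressive disease", limited to the period up to 30 November 2018. Section 6.3.2.2, on bone lesions, has the imaging technique chosen at baseline "and repeated until documentation of disease progression". Section 6.3 says "All trial procedures are detailed in the Schedule of Activities table presented below". That table (Table 9) marks disease assessment at screening and in the treatment period only; its End of Treatment cell and the whole survival row are empty.

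**After treatment.** Protocol section 6.2: "Once trial treatment is discontinued (both letrozole and afatinib) regardless of the reason, patients will be discontinued from the trial". Section 3 says the same of a patient who has had the End of Treatment visit. SAP section 3 instead sends her into a follow-up phase, and the OS definition in SAP section 4.1 mentions the end of a follow-up period.

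**Censoring.** SAP section 4.1 censors PFS at the last radiographic assessment, or at randomisation if there is none after baseline. TTP uses the same rules except that death is not an event.

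**Use of the results.** Protocol section 2.1.2 declares the objectives not applicable and plans description by arm without a statistical comparison. Section 8 refers the descriptive analysis to the SAP, which still lists PFS and TTP Kaplan-Meier output by arm.

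**The concern.** Two ends of observation for the primary endpoint, in one current protocol, would normally be a real defect. If imaging ends with treatment, a patient who stops for toxicity is censored at her last scan. If it continues to progression, she can still become an event. When such stops are related to prognosis, the first approach tends to flatter the arm with more of them.

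The routes out of treatment do differ by arm. Protocol section 5.3.3 lists triggers tied to afatinib dose reduction and to holding afatinib, which can arise only in arm B. Section 3 has a route that affects only arm A: once the arm B patients have stopped, "the patients from the other arm (arm A, letrozole alone) still on treatment will also be discontinued from the trial at the same time".

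There is also a sign that the rule changed over time. Section 5.1 says that randomised but untreated patients used to be followed, and then: "These patients will now be discontinued from the trial once their trial treatment is discontinued". The SAP does not say which observation window applied to whom. Its one named PFS sensitivity analysis (section 10.5.1) only adds censoring, so it cannot probe the question. At stake would be the reading of the PFS and TTP curves by arm.

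**Working it through.** **1. The plan's own figure.** SAP section 5.3 sets the final analysis at 127 PFS events. With medians of 9 and 14 months, two-sided 10% error, 80% power and 1:1 allocation (SAP sections 3 and 5.2): 4 × (1.645 + 0.842)² / [ln(9/14)]² = 24.73 / 0.1952 = 126.7, rounded up to 127. The figure reproduces. It has no bearing here, because the current protocol drops the comparison.

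**2. Who is affected.**

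| Patient | Imaging to progression | Imaging to end of treatment |
|---|---|---|
| Stops because of RECIST progression (the default in Protocol 5.3.3) | Event at progression | Same |
| Dies on treatment without progression | PFS event at death | Same |
| Stops alive without progression | Later scans, if made, extend observation | Censored at last on-treatment scan |

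Only the third row differs.

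**3. Which reading is current.** For end of treatment: section 6.3.2.1, Table 10, Table 9, and the removal from the trial in sections 3 and 6.2. For progression: one synopsis line and the bone-lesion note, whose subject is which imaging technique to keep using. The SAP was matched to a CRF of 29 January 2014. It still plans 150 subjects, whereas enrolment closed on 05 March 2016. Its follow-up phase is therefore pre-closure text.

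**4. Whether the censoring rule fails.** It does not. SAP section 4.1 refers to the last assessment and sets no cut-off at end of treatment. If a patient has later scans under an earlier protocol version, they count. If she has none, the last on-treatment scan is the date. For OS, section 4.1 censors at the last date known alive, and section 6 derives a last contact date from recorded dates, so losing the follow-up phase does not break that rule either.

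**5. Count.** Protocol section 1.4: "there are 6 patients still on treatment in the trial and among those, only 2 patients are treated with the combination" of letrozole and afatinib. So 6 − 2 = 4 were on letrozole alone.

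**6. Gap between scan and stop.** Scans fall every 12 weeks ± 1 week on a fixed calendar. The longest scheduled gap is (12(k+1) + 1) − (12k − 1) = 14 weeks. Any such schedule with last-scan censoring has this gap, so it does not measure the difference between the two wordings. Unscheduled scans for suspected progression can shorten it.

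**7. Arm-specific exits.** The section 5.3.3 hold trigger is not absolute. Section 5.4.1 allows a case-by-case decision for a patient with obvious clinical benefit, which includes stable disease or response at the last assessment. The arm A exit in section 3 is set off by other patients stopping, not by her own condition, so nothing suggests that it is informative. The alternative branch stops both arms on the same date.

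**8. Scale if the windows did differ (assumed inputs).** The documents give no rate of stopping without progression. Take an arm B on-treatment median of 14 months (hazard λ = ln 2/14 = 0.0495 per month). Let a share s stop without progression by 12 months (μ = −ln(1 − s)/12), with progression hazard k times λ afterwards. Imaging to end of treatment returns a median of 14.0 months. Imaging to progression gives, over k from 3 down to 1: 13.0 to 14.0 months (s = 10%), 12.1 to 14.0 (20%), 11.4 to 14.0 (30%). At k = 1 the two agree.

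**The case for a change.** The strongest case for a change is that descriptive curves are read comparatively whatever the protocol says, and that section 8 relies on an SAP whose design section contradicts the protocol. An outdated SAP explains the mismatch without curing it. If early arm B stops were related to later progression, step 8 shows that the arm B median could move by a month or more. No planned table cross-classifies PFS censoring by reason for stopping.

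Part of this stands. The mismatched wording is real, and the SAP is silent on whether the observation window changed by protocol version. The cross-tabulation is indeed absent.

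The rest does not lead to a change. Step 8 rests on assumed rates and assumed hazards. Its difference comes from scans made or not made after treatment, and editing a sentence now creates none. SAP section 10.1 and the Subject Disposition table already give reasons for stopping treatment and study by arm. The withdrawal and efficacy listings in section 11.2 link reason to outcome patient by patient. A cross-tabulation would only rearrange that information. An added analysis counting stops without progression as events would be closer to time to treatment failure and pessimistic for arm B by construction. It would also count clinical progression, which SAP section 4.1 excludes, and it could not show which window had applied.

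**Conclusion.** This is a clerical inconsistency, together with a small gap that analysts fill by applying the stated censoring rule to the recorded scans. End of treatment is the determinable current end of imaging. The synopsis line, the bone-lesion phrase and the SAP's follow-up phase are residual text. PFS and TTP censoring is defined, and no difference between arms is shown in size or direction.

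The present wording reaches at most the 6 patients on treatment when the amendment was released, 2 in arm B and 4 in arm A, in a closed trial with objectives declared not applicable and no comparison planned. Aligning the phrases would be good housekeeping if the documents were reopened, but it would alter no result and no conclusion.

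This rests on three assumptions: that all recorded scans and deaths are used as SAP section 4.1 directs; that the no-comparison statement in Protocol section 2.1.2 governs; and that patients who stopped earlier were handled under protocol versions that the documents do not show. If a comparison of arms were reinstated, the question would need to be reopened.
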